5.4. Assessment schedule

The summary of study assessments will be included in Appendix 1: Schedule of study assessments and procedures.

5.5. Discontinuation of patient, study, or site participation

Treatment discontinuation: Patients have the right to withdraw from the study at any time and for any reason, without being required to state their reasons for doing so. The investigator has the right to discontinue a patient from study treatment or from the study for any medical condition that the investigator determines may jeopardize the patient's safety if he continues in the study, for reasons of non-compliance (e.g., missed doses, visits), or if the investigator determines it is in the best interest of the patient.

Patients should also be withdrawn from the study treatment if they experience disease progression as defined by the RECIST criteria version 1.1. Further details regarding study discontinuation due to side effects are described in section 6.11.

Patients who withdraw from study treatment prematurely will be followed up in accordance to section 5.3 except for those patients who withdraw their consent and who do not wish to undergo a follow-up. The main reason for discontinuation should be recorded in the appropriate section in the CRF.

Study discontinuation:

Patients will be withdrawn from the study (e.g., from any subsequent study procedure) for any of the following reasons:

- Withdrawal of consent.
- Lost to follow-up.

If patient is lost to follow-up, site personnel must do their utmost to re-establish contact with the patient and determine the reason for their withdrawal. All measures taken to undertake follow-up should be recorded.

When a patient withdraws before the end of the study, the reason for withdrawal should be recorded in the CRF and in the original document. Patients who withdraw from the study will not be replaced.

In addition, the Sponsor reserves the right to terminate this study at any time. Reasons for terminating the study may include, but are not limited to, the following:

- The incidence or seriousness of AEs in this or other studies indicates a potential health risk to patients.
- Patient enrollment is unsatisfactory.
- Data recording is inaccurate or incomplete.

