A complete physical examination should include an examination of head, eyes, ears, nose, and throat as well as cardiovascular, dermatological, musculoskeletal, respiratory, digestive, genitourinary, and neurological systems. Changes to abnormalities identified during the baseline period should be recorded at all subsequent physical examinations. New or worsening abnormalities should be recorded as AEs, if applicable.

Physical exams should also include, as part of tumor assessment, evaluation of presence and degree of increase of lymph nodes, hepatomegaly, and splenomegaly. Limited physical exams will focus on symptoms.

Response and tumor assessments:

Tumor response will be assessed for all patients, unless they withdraw from the study for any reason not attributable to disease progression confirmed radiologically or clinically and who have not received an acceptable complete assessment of the disease. The non-measurable disease should be documented at screening and be re-assessed at every tumor assessment thereafter.

The initial assessment of tumor response will be performed at the end of cycle three. Subsequently, an efficacy follow-up will be carried out for all patients every 12 weeks ± 7 working days during the study until disease progression, the patient withdraws their consent, or death, whichever comes first. In this study, response and disease progression will be assessed using the PCWG2 guidelines for bone disease and the RECIST criteria version 1.1 for soft-tissue disease. Radiographic disease progression in bone will require persistence of new lesions on a confirmatory bone scan performed at least six weeks later. Soft-tissue progression will not require a confirmatory scan for purposes of analysis (Appendix 2: Response Evaluation Criteria in Solid Tumors Guidelines (RECIST criteria) version 1.1).

A torax, abdomen, and pelvis CT scan or MRI, and a bone scan must be performed at screening (no more than 28 days before the first trial treatment). Tumor assessments should include an assessment of all known and/or suspected sites of the disease wherever possible. Patients should have a series of selected lesions that can be assessed at each tumor assessment. The same radiographic procedure employed at screening should be used throughout the study (e.g., the use of the same contrast protocol for CT scans).

Laboratory assessments:

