8.3.1. Primary efficacy endpoint

The primary efficacy endpoint is the median PFS achieved with radium-223 treatment. The PFS will be evaluated at the first 34 months period of the study. The PFS will not be evaluated at the 2-years extension of the study for safety. PFS is a composite endpoint defined as the time from the start of the radium-223 treatment to disease progression in bone or soft-tissue, symptoms, or death, according to the modifiedPCWG2 criteria. Objective radiographic disease progression is defined as the presence of at least one of the following conditions:

- Bone lesion progression (appearance of \geq two new bone lesions compared to baseline).
- Soft-tissue lesion progression according to the RECIST criteria version 1.1.
- Presence of symptomatic skeletal events.

Patients with no progression will be censored at the date of their last evaluation. Censoring rules are specified in Table 2.

Table 2. Censoring rules for PFS

Situation	Date of progression or censoring	Outcome
Progression documented between scheduled visits	Earliest of: 
 
• Date of radiological assessment showing new lesion (if progression is based on new lesion); or 
• Date of last radiological assessment of measured lesions (if progression is based on increase in sum of measured lesions); or 
• Bone lesion progression (appearance of \geq two new bone lesions compared to baseline); or 
• Presence of symptomatic skeletal events (pathological fractures, spinal cord compression, radiation or surgery to bone) 	Progressed
Death before first progression disease assessment	Date of death	Progressed
Death between adequate assessment visits	Date of death	Progressed
No progression	Date of last radiological assessment of measured lesions	Censored
Treatment discontinuation for undocumented progression	Date of last radiological assessment of measured lesions	Censored
Treatment discontinuation for toxicity or other reason	Date of last radiological assessment of measured lesions	Censored
Death or progression after more than one missed visit	Date of last radiological assessment of measured lesions	Censored

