8.6. Missing data management

The analysis of the primary and secondary timed endpoints (progression and death) will be based on a Log-Rank or Cox regression tests and, therefore, not affected by patient withdrawals (as they will be censored) provided that dropping out is unrelated to prognosis. Patients with missing information in other outcomes, such as clinical benefit rate or overall response, will be considered as no responders. Furthermore, we will report reasons for withdrawal for each randomization group and compare the reasons qualitatively.

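### Section 5.5 contradicts itself on who may be removed from the whole study; where removal is related to prognosis, later events are lost and the condition in 8.6 fails

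*Protocol*

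**What the plan says.** Protocol 5.5 contains three rules on this point.

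- Its treatment-discontinuation paragraph states: "The investigator has the right to discontinue a patient from study treatment or from the study for any medical condition", where the investigator judges that remaining in the study may endanger the patient. It adds further grounds: "for reasons of non-compliance (e.g., missed doses, visits), or if the investigator determines it is in the best interest of the patient".
- A later paragraph of the same section states: "Patients who withdraw from study treatment prematurely will be followed up in accordance to section 5.3". The only exception is a patient who withdraws consent and does not want follow-up.
- The study-discontinuation paragraph states: "Patients will be withdrawn from the study (e.g., from any subsequent study procedure) for any of the following reasons". Two reasons follow: withdrawal of consent and loss to follow-up. It adds: "Patients who withdraw from the study will not be replaced".

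Protocol 5.2 states that "an efficacy follow-up will be carried out for all patients every 12 weeks", ending at progression, withdrawal of consent or death. Investigator removal is not among the end points. Protocol 3.2 lists adverse events and major non-compliance as reasons to stop treatment early, and its follow-up phase provides tumour re-evaluation for patients who stopped for a reason other than progression.

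On the analysis side, protocol 8.6 calls the time-to-event analyses "not affected by patient withdrawals (as they will be censored) provided that dropping out is unrelated to prognosis". Protocol Table 2 (8.3.1) and SAP Appendix I Table 1 have a row for "Treatment discontinuation for toxicity or other reason", which censors PFS at the last radiological assessment. OS is censored when the patient was last known alive (protocol 8.3.2, SAP 7.2.1 and 8.5).

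**The concern.** A site reading 5.5 cannot tell whether a patient taken off for a medical condition, missed visits or best interest stays in follow-up. Under the first rule he may leave all study procedures. Under the other two, and under 5.2, he may not.

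The choice matters because the trial has one arm and is judged against a fixed median PFS of 3 months, so no control group shares the loss. Site investigators assess the endpoint without central review (protocol 8.3.5), so the person who may remove a patient also reads his scans. If patients near progression or death are removed more often than others, their events are replaced by censored times and the hazard is underestimated. Neither document plans a sensitivity analysis for informative censoring.

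**Working it through.** **Inputs from the documents.** N = 52, one-sided alpha 0.05, 80% power, median PFS 3 months under the null and 6.3 months under the alternative, 23 months of accrual plus 11 of follow-up, 25% AR-V7-positive (protocol 8.2). The test is the exponential maximum-likelihood test (SAP 7.1.1), with scans every 12 weeks.

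**The plan's own figure.** Events needed: d = (1.645 + 0.842)² / [ln(3/6.3)]² = 11.23. With λ = ln 2 / 6.3, accrual A = 23 and follow-up F = 11, the event probability is 1 − [exp(−λF) − exp(−λ(F + A))] / (λA) = 0.892. Then 11.23 / 0.892 = 12.6, rounded up to 13 AR-V7-positive patients, and 13 / 0.25 = 52. The plan's figure reproduces. It contains no dropout term, so the fix does not change N.

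**Effect of removal on PFS.** Inputs assumed, because the documents give none: the share q of patients removed, and when. Simulation of 40,000 trials with N = 52, exponential PFS and a true median of 3 months, so that every positive result is false. Removed patients leave just before their event and are censored at the previous 12-week scan.

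| Share removed | Patients of 52 | Positive rate, removed just before event | Estimated median (months) | Positive rate, removal unrelated to event |
|---|---|---|---|---|
| 0 | 0 | 0.04 | 2.98 | 0.04 |
| 5% | 2.6 | 0.07 | 3.09 | 0.04 |
| 10% | 5.2 | 0.11 | 3.21 | 0.04 |
| 15% | 7.8 | 0.18 | 3.36 | 0.04 |

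The one-sample log-rank test, which the protocol names, gives rates within about 0.002 of these.

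**Hand check.** The exponential estimate of the median is ln 2 × total time / events. If a share q of events became censored at the event time itself, total time would stay the same and the estimate would be multiplied by 1/(1 − q): 2.98 / 0.95 = 3.14 and 2.98 / 0.90 = 3.31. Censoring at the previous scan also shortens the recorded time, so the shift in the table is somewhat smaller.

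**Which rule does the censoring.** For PFS there are two routes. Removal under 5.5 ends the scans. Separately, the table row on stopping for toxicity or another reason can be read as censoring a patient at treatment stop even if he is still scanned. For OS there is one route, because the OS tables have no treatment-stop row: deaths are lost only if survival contact ends.

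**The case against.** The strongest objection is that the PFS harm need not come from 5.5. On its plain reading, the Table 2 row censors a patient who stops treatment for a medical condition whether or not he also leaves the study. A reader might infer that deleting three words from 5.5 repairs PFS. The documents do not support that, because the edit could leave every PFS figure unchanged unless the tables are aligned too. This part of the objection stands. It does not excuse 5.5, since an event that is never collected cannot be recovered by any table or sensitivity analysis.

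Second, the clause on medical conditions is limited to those judged to endanger the patient, and it sits beside missed doses or visits and best interest. A reader might infer that every such removal is by nature related to prognosis. The text does not say so: some intercurrent illness or missed visits may be unrelated, and then the false-positive rate stays at about 0.04. This also stands.

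Third, the documents already protect much of the follow-up. The list in 5.5 does not say that it is exhaustive, 5.5 sends treatment stoppers to 5.3, 5.3 requires imaging within 28 days of the end of treatment, and deaths and skeletal events before removal count. One can read the sentence as loose wording with the operative rule further down. That is a fair account of the likely intent, but the sentence still conflicts with a follow-up rule whose only exception is withdrawal of consent.

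Fourth, the simulated case is unfavourable. Removal earlier than just before the event, or an end-of-treatment scan that catches progression, lowers the rates. The simulation also uses exact event times. If every event were dated at a 12-week scan, the test would already be positive roughly three times in four at a true median of 3 months. The figures therefore show the shift caused by removal, not this trial's actual error rate.

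**Conclusion.** The contradiction within 5.5, and between it and 5.2, is on the page and should be reconciled. Its consequence is conditional: if removal is related to prognosis, later progression, skeletal events and deaths go uncollected, the patient is censored, and the condition in 8.6 does not hold.

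For PFS, the false-positive rate rises from about 0.04 to about 0.07 with 5% of patients removed and about 0.11 with 10%. This is an upper range that rests on assumed removal shares, removal just before the event, and exact event times. How often removal would occur is unknown.

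For OS, the bias would be upward but is not quantified. A reader might carry the 3-month comparison over to OS, but that null applies to PFS only; OS is a secondary endpoint with no fixed benchmark.

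**What to change.** 1. In protocol 5.5, reconcile the passages so that the investigator's right covers study treatment only. State that patients stopped in this way continue scans, skeletal-event and survival follow-up under 5.3 unless they withdraw consent to follow-up. Keep withdrawal of consent and loss to follow-up as the only reasons for leaving the study.
2. In protocol Table 2 and SAP Appendix I Table 1, state that a patient who stops treatment for toxicity or another reason but is still scanned is not censored at treatment stop, and that later documented progression or death counts as an event.
3. Add a sensitivity analysis that counts patients removed without a recorded event as events at removal.

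The clinical grounds for stopping treatment are unchanged, and N stays at 52. The visits are already in 5.3 and Appendix 1, and contact after progression may be by telephone. The cost is two wording changes, one extra analysis and a few more visits or calls; the documents do not say how these are funded.

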6. STUDY DRUG INFORMATION

6.1. Study treatment

Once enrolled in the study, the patient will receive study treatment.

Patients will be treated with radium-223 at a dose of 55 kBq (1.49 microcurie) per kilogram body weight, given at four-week intervals for six IV injections.

6.2. Drug supply

The latest version of study document Summary of Product Characteristics (SmPC) for radium-223 (Xofigo[®]) includes updated information on this drug.

The Sponsor will provide radium-223, which will be manufactured by the contract manufacturer: Institute for Energy Technology, Isotope laboratories, Kjeller, Norway. The products will be produced according to Good Manufacturing Practice (GMP), and will be delivered in a glass vial,

ready-to-use, with a certified activity. Radium-223 will be shipped in a lead container and type A radioactive package according to international transportation guidelines for radioactive materials. The alpha-pharmaceutical radium-223 is a ready-to-use, sterile, non-pyrogenic, clear, and color less aqueous solution of $^{223}\text{RaCl}_2$ for IV administration. The product is isotonic and has a pH of 6.0-8.0 with a pre-calibration of 14 days.

Single-use vials contain 6 mL solution at concentration of 1100 kBq/mL (27 microcurie/mL) at the reference date with a total radioactivity of 6.6 MBq the reference date (after 2015 NIST implementation). When administered on a day other than the reference day, the volume should be corrected according to the physical decay table.

Radium-223 has a shelf life of 28 days from production day, when stored at ambient temperature. The shelf life has been demonstrated for temperatures from cold storage (2-8°C) up to 40°C. In addition, it has been shown that the product quality is not jeopardized upon freezing. All study drugs will be labeled according to the requirements of local law and legislation. Label text will be approved according to the Sponsor's agreed procedures.

For all study drugs, a system of numbering in accordance with all requirements of GMP will be used, ensuring that each dose of study drug can be traced back to the respective bulkware of the ingredients. Lists linking all numbering levels will be maintained by the Sponsor. A complete record of batch number and expiry dates for all study treatments as well as the labels will be maintained in the Sponsor study file.

Once the study has ended, patients may continue receiving commercial radium-223, if it is found to offer clinical benefits in the opinion of the investigator

6.3. Dosage and administration

Written information about radium-223 and instruction about handling and injection of radioactive material will be provided to study personnel.

In general, the administration of radioactive drugs involves a potential risk for third parties, due to radiation from the patient and due to possible contamination by spilling urine or feces. When radium-223 has been injected intravenously into a patient, the risk for external radiation exposure to third parties is extremely low, due to the short range of the alpha particles and the low portion of beta and gamma radiation. For these reasons the product can be administered on an out-patient basis. To minimize the risk of contamination, the patient and his caregivers will receive instructions regarding hygiene precautions to abide by after receiving the radioactive drug according to the investigational site radiation protection guidelines.

6.4. Dose calibration

Radium-223 can be measured in a normal dose calibrator instrument. When written approvals for the use of radium-223 from the Radiation Protection Agency for the specific center have been received by the Sponsor, a vial of radium-223 for technical use will be sent to the study center. Different clinical study centers possess dose calibrators from various suppliers; thus,

the isotope calibration factor may differ from center to center. Consequently, each center must perform the radium-223 dial setting on their relevant dose calibrator(s). For dial setting, the clinical study center will receive a sealed vial containing a radium-223 solution for calibration only. The vial is identical to the vials used for study treatment. The amount of radium-223 in the vial will be stated on the label. Instructions for the dial setting, including the calibration log form, will be enclosed with the dispatch of the calibration sample.

6.5. Dose handling

Ordering of study drug will be done using Drug Order Form, the site will send this request to MedSIR before each planned administration and MedSIR will manage the study drug shipment with Bayer. The radium-223 vials must be stored inside their lead container in a secure facility. The study drug should be used within 28 days of production.

Radium-223 is an alpha-emitting pharmaceutical and should be received, used and administered only by authorized persons in designated clinical settings. The receipt, storage, use, transfer, and disposal are subject to the regulations and/or appropriate licenses of the competent official organization. Radiopharmaceuticals should be prepared by the user in a manner which satisfies both radiation safety and pharmaceutical quality requirements. Appropriate aseptic precautions should be taken.

Control measurements of both the radium-223 vial (before and after dispensing) and syringes (before and after administration) are performed as part of the clinical trial documentation. All administrations of radium-223 are based on the certified activity of radium-223 at the calibration date.

6.6. Dose calculation

The dosage of radium-223 is 55 kBq per kilogram body weight. The total activity to be injected will be calculated volumetrically using the patient's body weight on the day of injection, the 55 kBq per kilogram body weight dosage level, and the decay correction factor (DK) to correct for physical decay of radium-223 (after NIST implementation). A table with DKs according to physical decay of the study medication will be provided with each vial of radium-223. The total amount (volume to be drawn into the syringe) to be administered to a patient should be calculated as follows:

$$\frac{\text{Body weight (kilograms)} \times 55 \text{ kBq per kilogram body weight}}{\text{DK} \times 1100 \text{ kBq/ml}} = \text{Volume to be injected (mL)}$$

6.7. Dose preparation

Personnel should use appropriate protective clothing and equipment during syringe filling and application to prevent contamination with the radioactive solution (lab coats, medical gloves/protective glasses). Sites should adhere to all relevant radiation safety regulations as prescribed by local authorities administering their site radiation license, including ALARA principles.

Filling of the syringe should take place in a safetybench or similar cabinet in the Radiopharmacy/Nuclear Medicine department. The individual responsible for study drug preparation will draw the correct volume of study drug into a syringe. The size of the syringe should be chosen according to the applied volume to reach the required dosing accuracy.

Radium-223 should not be diluted or mixed with any solutions. If the vials have been stored in a refrigerator, they should be left at room temperature for one hour prior to use, since cold material should not be injected in a patient.

6.8. Dose administration

Before administration of study drug, the patient must be well hydrated and should be instructed to drink ad libitum. Aseptic technique should be used in the administration of radium-223. The syringe should be handed over to the individual who will perform the injection. The study medication will be administered as a slow bolus IV injection over one minute. After administration, the equipment used in connection with the preparation and administration of drug is to be treated as radioactive waste and should be disposed in accordance with hospital procedure for the handling of radioactive material. Information about radium-223 and instruction about handling and injection of radioactive material will be given to study personnel.

